APPENDIX E: STUDY PRODUCT PREPARATION PROTOCOL	87
APPENDIX F: GUIDELINES FOR SYMPTOM MANAGEMENT DURING STUDY PRODUCT INFUSION	103
APPENDIX G. MINI-BRONCHOALVEOLAR LAVAGE PROCEDURE	106
APPENDIX H. PHASE 2B INVESTIGATIONAL PRODUCT INFUSION PROTOCOL	107
APPENDIX I. BAROTRAUMA	112
APPENDIX J. CHILDS-PUGH SCORE FOR LIVER DYSFUNCTION.....	113
APPENDIX K. ORDINAL SCALE FOR CLINICAL IMPROVEMENT (OSCI).....	114
APPENDIX L. RADIOGRAPHIC ASSESSMENT OF LUNG EDEMA (RALE) SCORE.....	115

1 Protocol Synopsis

Name of Sponsor – Investigator	[name] University of California, San Francisco
Investigational Product	Allogeneic Bone Marrow-derived Human Mesenchymal Stromal Cells (hMSCs)
Protocol Number:	UCSF-hMSC-ARD-P1P2-14
Title:	A Phase 2b, Randomized, Double-blind, Placebo-controlled, Multi-center Clinical Trial of Allogeneic Bone Marrow-Derived Human Mesenchymal Stromal Cells for the Treatment of Acute Respiratory Distress Syndrome
Short Title	Mesenchymal Stromal Cells For Acute Respiratory Distress Syndrome
Clinical Phase	Phase 2b
Methodology	Randomized, double-blind, placebo-controlled
Study duration	3-4 years
IND Sponsor-Investigator	[name]
Funding Sponsor	Department of Defense
Study Product	Allogeneic Bone Marrow-derived Human Mesenchymal Stromal Cells (hMSCs)
IND Number	15331
Participating Sites	Intensive Care Units at seven Clinical Centers: Zuckerberg San Francisco General Hospital & Trauma Center and UCSF Moffitt-Long Hospital (San Francisco, CA), University of California Davis Medical Center (Sacramento, CA), Harborview Medical Center (Seattle, WA), Oregon Health & Science University (Portland, OR), Vanderbilt University Medical Center (Nashville, TN) and the University of Texas Health Sciences Center at Houston/Memorial Hermann-Texas Medical Center (Houston, TX)
Study Objective	To assess the efficacy of hMSCs in critically ill patients with Acute Respiratory Distress Syndrome (ARDS)
Accrual Objective	120 patients (60 patients receiving hMSCs and 60 patients receiving placebo)

Name of Sponsor – Investigator	[name] University of California, San Francisco
Investigational Product	Allogeneic Bone Marrow-derived Human Mesenchymal Stromal Cells (hMSCs)
Study Design	Randomized, double-blind, placebo-controlled, multi-center. Subjects with ARDS will receive a single infusion of hMSCs or placebo.
Study Product, Dose, Route, Regimen	
The cellular product is cryopreserved for long-term storage. The cryopreserved hMSCs are formulated in CryoStor (90%) and DMSO (10%).
 
Immediately prior to administration, the product is thawed and diluted in 1:1 reconstitution media (1:1 mix of 5% human serum albumin and 10% Dextran 40). Additional reconstitution media is added to a final product volume of 300 mL.
 
Placebo: 300 mL of reconstitution media (1:1 mix of 5% human serum albumin and 10% Dextran 40).
 
Each dose of the hMSCs or placebo will be administered intravenously over approximately 60-80 minutes. All patients will receive one dose. ×
 
10 x 10⁶ cells/kg (n=60); placebo (n=60)

Primary Endpoint:	Reduction in the severity of ARDS: Change in the oxygenation index (OI) from baseline over 36 hours following the initiation of study product infusion (with measurements of OI at 6, 12, 18, 24, 30 and 36 hours).
Secondary Endpoints:	
Respiratory physiology endpoints: The 4-point acute lung injury score (LIS) at days 1, 2, 3 and 7, or on the last day of positive pressure ventilation prior to day 7; pulmonary dead space at days 1, 2, 3 and 7; chest radiograph assessment of pulmonary edema (RALE score) at days 1, 2, 3 and 7; ventilatory ratio with measurements at 6, 12, 18, 24, 30, and 36 hours, and days 2, 3, and 7; incidence of barotrauma at days 1, 2, 3 and 7; ventilator free-days over 7, 14 and 28 days; duration of assisted ventilation over 28 days in the survivors; achieving pressure support ventilation equal to 5 cm H₂O with positive end-expiratory pressure (PEEP) equal to 5 cm H₂O for 2 hours. OI will be collected (as planned) also on days 2, 3, and 7 if still being ventilated with positive pressure as a secondary endpoint.
 
Secondary Infection endpoints: Superficial incisional/wound infections, deep incisional wound infections, and organ/space infections, and ventilator associated pneumonia (all during the 14

Name of Sponsor – Investigator	[name] University of California, San Francisco
Investigational Product	Allogeneic Bone Marrow-derived Human Mesenchymal Stromal Cells (hMSCs)
	
days after enrollment).
 
Systemic illness endpoint: Sequential Organ Failure Assessment (SOFA) score at 3, and 7 days; in hospital mortality at 14, 28 and 60 days; additional prognostic value of neutrophil:lymphocyte ratio; ordinal scale for clinical improvement at 7, 14 and 28 days.
 
Neurocognitive endpoint: Neurocognitive function measured by the Glasgow Outcome Score at hospital discharge
 
Thromboembolic: Incidence of thromboembolic events measured by ultrasound of the deep venous system or CT-angiography of the chest ordered for clinical purposes/by treating clinicians; additional prognostic value of fibrinogen at baseline.
 
Biomarkers:
 
Plasma: Change in levels of plasma, urine and genetic biomarkers from baseline compared to 6, 24, 48, and 72 hours including: endothelial injury (angiopoietin-2), lung epithelial injury (Receptor for Advanced Glycation Endproducts [RAGE]), pro-inflammatory pathways (interleukin-6 [IL-6], interleukin-8 [IL-8], soluble tumor necrosis factor-1 [sTNF-1], intercellular adhesion molecule-1 [ICAM-1], interferon gamma-induced protein-10 [IP-10], interleukin-10 [IL-10], vascular endothelial growth factor [VEGF], matrix metalloproteinase-8 [MMP-8], thrombomodulin, surfactant protein-D [SP-D], triggering receptor expressed on myeloid cells-1 [TREM-1], interleukin-18 [IL-18], plasminogen activator inhibitor-1 [PAI-1]), impaired coagulation (protein C), pro-resolving lipids (lipoxin A4, Resolvin D₁), biomarkers that reflect the paracrine activity of the administered hMSCs (angiopoietin-1 [Ang-1] and keratinocyte growth factor [KGF]). Changes in levels of plasma SARS-CoV-2 viral antigen and antibody levels at multiple timepoints; gene expression at baseline and on day 2 and 3.
 
Alveolar fluid: Lung protein permeability as measured by total protein in mini-bronchoalveolar lavage [mBAL] protein at day 2; the same biomarkers will also be measured in plasma to compare hMSCs versus placebo treated patients.
 
Urine: Microalbumin will also be measured at 24 and 48 hours
 
Others: Primary and secondary endpoints will be adjusted by SARS-CoV2 infection to better understand the hMSC effects in patients with COVID-19 disease.

Name of Sponsor – Investigator	[name] University of California, San Francisco
Investigational Product	Allogeneic Bone Marrow-derived Human Mesenchymal Stromal Cells (hMSCs)
	Safety endpoints: Tolerability of the hMSCs, defined as the incidence of pre-specified infusion-associated events and unexpected severe adverse events in ARDS patients treated with hMSCs.
Inclusion Criteria	
Patients will be eligible for inclusion if they meet all of the below criteria within 14 days of initial ICU admission. Criteria 1-3 must all be present within a 24-hour time period and at the time of enrollment:
 
Acute onset (defined below) of:
 
1. A need for positive pressure ventilation by an endotracheal or tracheal tube with a $\text{PaO}_2/\text{FiO}_2$ ratio <250 mmHg and ≥ 5 cm H_2O positive end-expiratory airway pressure (PEEP), as per the Berlin Criteria.2. Bilateral infiltrates consistent with pulmonary edema (defined below) on the frontal chest radiograph, or bilateral ground glass opacities on a chest CT scan.3. No clinical evidence of left atrial hypertension as a primary explanation for the bilateral pulmonary infiltrates.4. If the cause of ARDS is trauma, additional inclusion criteria will include ONE of the following relevant risk factors for developing ARDS:
a. Hypotension (systolic blood pressure [SBP] < 90 mmHg) in the field or in the first 24 h after injury, orb. Transfusion of 3 units of blood products in the first 24 hours following injury, orc. Meets the new Critical Administration Threshold (CAT) criteria with at least 3 units of blood in one hour, ord. Blunt or penetrating torso trauma, ore. Long bone fractures, orf. The highest level of institutional trauma activation 
ARDS Diagnostic Criteria Defined:
 
• Acute onset is defined as follows: The duration of the hypoxemia criterion (#1) and the chest radiograph criterion (#2) must both be present ≤ 14 days of initial ICU admission at the time of enrollment

Name of Sponsor – Investigator	[name] University of California, San Francisco
Investigational Product	Allogeneic Bone Marrow-derived Human Mesenchymal Stromal Cells (hMSCs)
	
• Infiltrates considered “consistent with pulmonary edema” include any infiltrates not fully explained by mass, atelectasis, or effusion or opacities known to be chronic (>14 days of initial ICU admission). Vascular redistribution, indistinct vessels, and indistinct heart borders alone are not considered “consistent with pulmonary edema” and thus would not count as qualifying opacities for this study.• If a patient meets #1 and #2 inclusion criteria but has an echocardiogram with LV ejection < 40% ordered by treating clinicians because of a clinical suspicion of acute left heart failure, the patient will be excluded.• If the patient meets #1 and #2 inclusion criteria but has a Pulmonary Arterial Occlusion Pressure (PAOP), also known as the Pulmonary Arterial Wedge Pressure (PAWP), that is initially greater than 18 mm Hg, then the inclusion criteria must persist for more than 12 hours after the PAOP has declined to ≤ 18 mm Hg.
Exclusion Criteria	
1. Age less than 18 years2. Greater than 72 hours since first meeting ARDS criteria per the Berlin definition of ARDS3. Greater than 14 days since initial ICU admission4. Inability to administer study product within 14 days of initial ICU admission5. $\text{PaO}_2/\text{FiO}_2 \geq 250$ mmHg after consent obtained and before study product is administered6. Unable to obtain informed consent/no surrogate available7. Pregnant or lactating8. In custody of law enforcement officials9. Burns > 20% of total body surface area10. WHO Class III or IV pulmonary hypertension11. History of cancer treatment in the last 2 years except for non-melanotic skin cancers12. Underlying medical condition for which 6-month mortality is estimated to be > 50%13. Moribund patient not expected to survive 24 hours

Name of Sponsor – Investigator	[name] University of California, San Francisco
Investigational Product	Allogeneic Bone Marrow-derived Human Mesenchymal Stromal Cells (hMSCs)
	
14. Advanced chronic liver disease (Childs-Pugh Score > 12)15. Severe chronic respiratory disease with the use of home oxygen16. Severe traumatic brain injury - defined as:
a. A patient who has undergone intracranial neurosurgical intervention for monitoring or therapy (intracranial pressure monitoring, external ventricular drain, craniotomy), orb. Intracranial injury by head CT (does not include patients with minimal subarachnoid injury and/or minor skull fracture), orc. Post-resuscitation Glasgow Coma Score (GCS) < 9 assessed after sedation interruption, ord. Non-survivable head injury as assessed by neurosurgery17. Evidence of anoxic brain injury18. History of stroke within the last 3 years19. No intent/unwillingness to follow lung protective ventilation strategy20. Currently receiving extracorporeal life support (ECLS) or high-frequency oscillatory ventilation (HFOV)21. Anticipated extubation within 24 hours of enrollment22. Clinical evidence of left atrial hypertension as measured by a pulmonary arterial wedge pressure > 18mmHg or left ventricular failure measured by an echocardiogram with a left ventricular ejection fraction less than 40%. Clinical judgement will determine if either of these measurements needs to be carried out.
Statistical Consideration	The primary endpoint, Oxygenation Index (OI), will be assessed for the change from the baseline measurement (prior to infusion of the study product) over 36 hours (with measurements at 6, 12, 18, 24, 30 and 36 hours), and will be compared between the placebo and hMSCs treatment conditions using a linear mixed-effects regression model. The model will be estimated using likelihood estimation which will allow the inclusion of all collected data, regardless of the number of assessments available for variable. Terms in the model will include the two stratification

Name of Sponsor – Investigator	[name] University of California, San Francisco
Investigational Product	Allogeneic Bone Marrow-derived Human Mesenchymal Stromal Cells (hMSCs)
	
variables, treatment condition (active or placebo), time of assessment, condition-by-time, recruitment site, and a site-by-treatment interaction term. A test of the treatment condition will directly test the main research question. Covariates identified by preliminary analysis as potentially confounding due to baseline differences will be added to the model.
 
Given the sample size of 60 per treatment condition, in this multisite, randomized trial using oxygenation index as the primary outcome and measures taken at 6 time points, it is estimated the study will have 80% power to detect a difference between conditions for an effect size as low as 0.43. Using the pilot data from Day 4, for example, this would translate to approximately a difference of 1.29 on the oxygenation index.
 
The primary and secondary endpoints (including clinical and biological data) will be adjusted for SARS-CoV-2 infection as a cause of ARDS, which is adjudicated by the study physicians.

2 Glossary of Abbreviations

Abbreviation	Full Term
AE	Adverse Event
AFC	Alveolar Fluid Clearance
ALI	Acute Lung Injury
ARDS	Acute Respiratory Distress Syndrome
mBAL	Mini-Bronchoalveolar Lavage
CFR	Code of Federal Regulations
cIRB	Central Institutional Review Board
CRF	Case Report Form
DoD	United States Department of Defense
DSMB	Data and Safety Monitoring Board
EAP	Expanded Access Program
ECMO	Extracorporeal Membrane Oxygenation
EUA	Emergency Use Authorization
FDA	Food and Drug Administration
GCS	Glasgow Coma Score
HFOV	High-Frequency Oscillatory Ventilation
HIPPA	Health Insurance Portability and Accountability Act of 1996
hMSCs	Human Mesenchymal Stromal Cells
HS	Hemorrhagic Shock
HSC	Hematopoietic Stem Cells
ICH	International Conference on Harmonization
ICU	Intensive Care Unit
IND	Investigational New Drug
IRB	Institutional Review Board
IV	Intravenous(ly)
KGF	Keratinocyte Growth Factor
LIS	Lung Injury Score
mBAL	Mini Bronchoalveolar Lavage
MSCs	Mesenchymal Stromal Cells
NIH	National Institute of Health
NHLBI	National Heart, Lung and Blood Institute

Abbreviation	Full Term
NLR	Neutrophil:Lymphocyte Ratio
OI	Oxygenation Index
OSCI	Ordinal Scale for Clinical Improvement
PACT	Production Assistance for Cellular Therapy
PAOP	Pulmonary Artery Occlusion Pressure
PBW	Predicted Body Weight
PEC	Pulmonary Endothelial Cell
PEEP	Positive End-Expiratory Pressure
PHI	Protected Health Information
SAE	Serious Adverse Event
SOP	Standard Operating Procedure
VR	Ventilatory Ratio

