Appendix A: Time-Events Schedule

Measurement/Event	Prior to randomization	Day 0	During and after MSC infusion	1	2	3	4	5	6	7	8	9	10	11	12	13	14	28	60	6m
Demographics, History & Physical, Height, Weight	X																			
Etiology of ARDS	X																			
HCG (in females of childbearing age < 50 years old)	X																			
Baseline stability assessment (Vital signs and ventilator parameters) ^{S,B}		X																		
Mechanism of injury and trauma registry index (if applicable)	X																			
APACHE III Score ^C	X																			
ECHO ^D	A																			
COVID-19 test	A																			
COVID-19 vaccination status	A																			
Co-enrollment with other clinical trials and COVID-19 related therapies ^M	X			A	A	A	A	A	A	A	A	A	A	A	A	A	A	A		
Vital Signs (HR, SBP, DBP, MAP, Temp °C, SpO2) ~\$	X	X	X	X	X	X	X	X	X	X	X	X	X	X	X	X	X	X		
Central Venous Pressure ~\$	A	A	A	A	A	A	A	A	A	A	A	A	A	A	A	A	A	A		
Record vasoressors or inotropes * (Y/N)S	X	X	X	X	X	X	X	X	X	X	X	X	X	X	X	X	X	X		
Fluids in/out, crystalloids, PRBC, FFP, platelets, cryoprecipitate, urine output	X	X	X	X	X	X	X	X	X	X	X	X								
Modified Brussels Score and Brussels Organ Dysfunction Failure~E	X			X	X	X	X	X	X	X	X	X	X	X	X	X	X	X		
Sequential Organ Failure Score	X																		X	
Ventilator Parameters (including FiO2) #	X	X	X	X	X	X	X	X	X	X	X	X								
Arterial Blood Gases (PaO2, PaCO2, pH, SpO2, base deficit)&	X	X	X	X	X	X	X	A	A	A	A	X								
Chest X-ray (# quadrants for lung injury score, RALE score)	A			A	A	A	A	A	A	A	A	A	A	A	A					
Pulmonary dead space ^F	X							X	X	X										
Creatinine%G,H	X							A	A	X	A	A	A	X	A	A	A	A	A	
Total bilirubin, ALT, platelets%H	X							A	A	X	A	A	A	X	A	A	A	A	A	
D-dimer, lymphocyte count, neutrophil counts, fibrinogen, ferritin and serum C-reactive protein (if applicable)	A	A		A	A	A	A	A	A	A	A	A	A	A						
Glasgow coma score ^I	X	X						X	X	X									X	
Outpatient medication and on-study medication and study procedure ^K	X							X	X	X	X	X	X	X						
DVT Prophylaxis medication [¶]	X	X	X	X	X	X	X	X	X	X	X	X	X	X	X	X	X	X		
Positive blood culture [¶]	X							X	X	X	X	X	X	X	X	X	X	X		
Thromboembolic complications [¶]	X							X	X	X	X	X	X	X	X	X	X	X		
Wound site infection and VAP assessment ^E	X							X	X	X	X	X	X	X	X	X	X	X		
Blood for cytokines, mediators and markers of inflammation ^N		X	X	X																
Blood for DNA/RNA		X																		
Urine for biomarker measurements ^O		X																		
Mini-BAL																				

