12.7.5 Additional Prognostic value of neutrophil-to-lymphocyte ratio

Neutrophil-to-lymphocyte ratios (NLR) will be calculated at baseline, days 1, 2, 3, 7, and summarized in modified ITT populations and in patients with confirmed COVID-19, stratified by the allocated groups. If NLR is skewed, log transformation will be applied to create normally

distributed data. The predictive values of NLR at baseline for poor clinical outcomes, including hospital mortality by day 28 and day 60, will be assessed using the receiver operating characteristic (ROC) curve and the optimal cutoff values of NLR will be determined using Youden's index.

To further evaluate the additional prognostic values of NLR on hospital mortality by day 28 and day 60, we will perform multivariate logistic Cox regression models which includes: baseline NLR value, $\text{PaO}_2/\text{FiO}_2 < 150$ mmHg or ≥ 150 mmHg, trauma vs. non-trauma, study product assignment and any baseline parameters that suggests the evidence of randomization imbalance between two treatment groups. This model will also be further conducted in the subgroup of patients with COVID-19 as a cause of ARDS, which is adjudicated by the study physicians.

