12.7.9 Additional prognostic value of baseline fibrinogen

Baseline fibrinogen will be summarized by median with interquartile range. If it is skewed, log transformation will be applied to create normally distributed data. The predictive values of baseline fibrinogen for poor clinical outcomes, including hospital mortality by day 28 and day 60, will be assessed using the receiver operating characteristic (ROC) curve and the optimal cutoff values of fibrinogen will be determined using Youden's index.

To further evaluate the additional prognostic values of baseline fibrinogen on hospital mortality by day 28 and day 60, we will perform multivariate logistic Cox regression models which includes: baseline fibrinogen value, $\text{PaO}_2/\text{FiO}_2 < 150$ mmHg or ≥ 150 mmHg, study product assignment and any baseline parameters that suggests the evidence of randomization imbalance between two treatment groups. This model will also be performed in the subgroup of patients with COVID-19.

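### Any sensitivity, specificity or Youden index reported at the NLR and fibrinogen cut-offs will be optimistic, because each cut-off is chosen and read in the same patients

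*Protocol*

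**What the plan says.** The Protocol Synopsis (Secondary Endpoints) names the endpoint without a method: "in hospital mortality at 14, 28 and 60 days; additional prognostic value of neutrophil:lymphocyte ratio". Baseline fibrinogen appears in the same way under the thromboembolic endpoints. Protocol 6.2.1 and SAP 7.2.1 repeat both.

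The method is in SAP 12.7.5 (NLR) and 12.7.9 (fibrinogen), which are worded almost alike. Each has two steps.

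1. The baseline marker's ability to predict hospital mortality by day 28 and day 60 is "assessed using the receiver operating characteristic (ROC) curve". Then, for NLR, "the optimal cutoff values of NLR will be determined using Youden's index"; for fibrinogen, "the optimal cutoff values of fibrinogen will be determined using Youden's index".
2. For additional prognostic value, a multivariable model is fitted. For NLR: "we will perform multivariate logistic Cox regression models which includes: baseline NLR value". The fibrinogen model likewise takes the baseline value. These models are repeated in patients with COVID-19.

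Neither section mentions a hold-out sample, cross-validation, bootstrap or optimism correction, and neither says whether high or low values count as adverse. Protocol Appendix A schedules the underlying laboratory values only where available, so fewer than 120 patients may contribute.

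**The concern.** Youden's index selects the cut-off at which sensitivity plus specificity is largest in the observed data. Part of that maximum is chance. If performance is then read at the same cut-off in the same patients, it overstates what the cut-off would achieve elsewhere. The cut-off itself is also poorly determined with a few dozen deaths.

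At stake is the description of two named secondary endpoints. A cut-off published as optimal may be reused in later studies, together with performance figures that will not hold there.

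**Working it through.** **The plan's own figure.** There is none to reproduce: neither document gives an AUC, a cut-off or a precision target for either marker.

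**Inputs.**
- Sample size: 120 (SAP 10).
- Mortality: 25-40% for the target population (Protocol 3.7.1), so 0.25 × 120 = 30 to 0.40 × 120 = 48 deaths. The Phase 2a results in Protocol 3.6 fit the lower end: 30% of 40 plus 15% of 20 is 12 + 3 = 15 deaths in 60, or 25%.
- Low-end check: 15%, the Phase 2a placebo mortality, so 18 deaths.
- Reduced sample: 80. This is an assumption, since the share of missing markers is not given.

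**Model.** Marker ~ N(0,1) in survivors and N(μ,1) in deaths, with μ = √2 × Φ⁻¹(AUC). For AUC 0.50, μ = 0. For AUC 0.65, μ = 1.414 × 0.385 = 0.545.

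**Quantities.**
- J(c) = P(marker > c | death) - P(marker > c | survivor).
- The chosen cut-off ĉ maximises the observed J(c). Apparent J is that maximum.
- J in new patients at the chosen cut-off is Φ(ĉ) - Φ(ĉ - μ).

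**Simulation results** (means; direction fixed so that higher is worse):

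| Setting | True AUC | Apparent J | J in new patients | Mean AUC |
|---|---|---|---|---|
| n = 120, 30-48 deaths | 0.50 | 0.11-0.12 | 0 | 0.50 |
| n = 120, 30-48 deaths | 0.65 | 0.29-0.30 | 0.19-0.20 | 0.65 |
| n = 120, 18 deaths | 0.50 | 0.15 | 0 | 0.50 |
| n = 80, 15-40% mortality | 0.50 | 0.13-0.18 | 0 | 0.50 |

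In the first row the 95th percentile of apparent J is 0.22-0.24. If the direction is also picked from the data, mean apparent J there rises to about 0.16-0.17 and the mean AUC to 0.54-0.55. In the second row the optimism is about 0.30 - 0.20 = 0.10, a third of the apparent figure.

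**Stability of the cut-off.** With true AUC 0.60, 30 deaths and 90 survivors, the middle 90% of chosen cut-offs runs from about the 23rd to the 89th percentile of the survivors' distribution.

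**The regression step.** For a useless marker at the two-sided 5% level:
- Baseline value kept continuous: rejected in 4.6-5.3% of runs (single-variable test) and 5.1-6.4% (multivariable logistic).
- Marker split at its own Youden cut-off: 20-24% (direction fixed), 37-41% (either direction) and 39-41% (multivariable).

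The multivariable rates are approximate. Covariate effects were assumed and some fits gave convergence warnings.

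**Does the remedy work?** I bootstrapped the whole search with 30 deaths and 90 survivors (200 data sets, 200 resamples each). Mean J for a useless marker fell from 0.12 to 0.04, removing 0.08 of the 0.12 bias. At AUC 0.65 it fell from 0.30 to 0.23 against a true 0.195, removing 0.07 of 0.105. Both are about two thirds.

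**The case against.** The case against has real force, and most of it stands.

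- **Discrimination by AUC.** A reader might infer that discrimination as a whole is inflated. The SAP's named tool is the ROC curve, whose area uses no cut-off, and mean AUC was unbiased in the simulations. It drifts upward only if the marker's direction is also chosen from the data, which the SAP leaves open.
- **A useless marker passing as prognostic.** A reader might also infer this. The SAP addresses additional prognostic value through a model containing the baseline value, and that test stays near 5%. The 20-41% rates need the marker to be split at the cut-off. The SAP does not state this, though it does not rule it out.
- **COVID-19 patients.** It is tempting to say that the cut-off search is repeated in a small COVID-19 subgroup. The SAP repeats only the regression there, and Protocol 3.1 says that the vast majority of enrolled patients had COVID-19.
- **What will be reported.** The SAP says that cut-offs will be determined; it does not say that sensitivity and specificity at them will be tabulated. The bias therefore applies to whatever is reported at the cut-off.
- **Exploratory status.** SAP 12.5 calls the secondary endpoints supportive and exploratory. That lowers the stakes. But the statement is there to justify not adjusting for multiple testing; it neither corrects a biased estimate nor marks the cut-off as provisional.

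**Conclusion.** The concern holds in a narrow form and is minor. The plan states a procedure whose cut-off performance is biased upward: J overstated by about 0.11-0.12 for a useless marker and by about 0.10 at a true AUC of 0.65, with 120 patients and 30-48 deaths. The cut-off itself is unstable.

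These sizes assume that all 120 patients have the marker, that in-hospital mortality falls in the range in Protocol 3.7.1, and that direction is fixed. Fewer patients, fewer deaths or a free choice of direction makes the optimism larger. The result for a useless marker does not depend on the normal shape, because the ROC curve uses only ranks; the result at AUC 0.65 does.

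The documents do not support any wider claim about the AUC, the multivariable test on the baseline value, or the primary oxygenation index comparison.

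**What to change.** In SAP 12.7.5 and 12.7.9:

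- Report the AUC with its confidence interval as the measure of discrimination, and state in advance which direction of each marker is adverse.
- Bootstrap the whole procedure, repeating the cut-off search in every resample. Give optimism-corrected sensitivity, specificity and J, with a bootstrap interval for the cut-off.
- Label the cut-off exploratory, since the bootstrap removes most of the bias but not all of it.
- Confirm that the regression models use the continuous marker (log-transformed if skewed, as already planned), not the marker split at its cut-off.

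The cost is a few sentences in the SAP and a few lines of code, with no new data and no design change. The reported cut-off performance will look less favourable.
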